8.3.3 PET

Fluorodeoxyglucose F18 (FDG)

The FDG PET procedure will utilize the CU-RIC research PET scanner for human imaging studies. The Philips Gemini 64TF PET/CT imaging system is located in Biosciences 3 on the Anschutz Medical Campus at the University of Colorado. An additional GE Signa PET/MR imaging system is also located within the CU-RIC for use as necessary.

Fluorodeoxyglucose F18 (FDG) is an FDA approved radiotracer that has been used extensively to evaluate glucose metabolism within many organs within the body, and in relation to the brain, FDG PET has been at the forefront of functional neuroimaging over the past 3 decades, used to measure local cerebral metabolic rate of glucose that is indicative of synaptic activity in the brain, and contributing to the understanding of cognitive functions in healthy humans and how these functional patterns change with cognitive alterations. FDG has also been approved by the FDA for the identification of regions in human brain of abnormal glucose metabolism associated with foci of epileptic seizures, as well as being used as a useful biomarker of the regional reductions in glucose metabolism associated with the different forms of dementia. Evaluation of regional brain metabolism with FDG, might also prove useful or necessary to make a diagnosis, particularly in difficult or atypical cases. Perhaps FDG's best use may be in combination with other neuroimaging modalities, such as with structural MRI (sMRI) analyses and in relation to AD, to help predict conversion of mild cognitive impairment (MCI) to AD. The FDG PET scans will be performed at baseline and at EOT Visit.

FDG PET Imaging Procedure

Prior to the visit, participants will be asked to abstain from food or drinks for 4 hours before the procedure. Each study visit will take approximately 2 hours. A 5-10 mCi intravenous injection of fluorodeoxyglucose F18 will be administered. After the fluorodeoxyglucose F18 dose is injected, a 3-5 minute head CT scan will be performed to aid in alignment and calibration, and adjust for attenuation effects. Dynamic images will be acquired for approximately 20-30 minutes. The IV catheter will be removed at the conclusion of the scan and materials will be disposed of in biohazard containers or decay chambers until they can be safely disposed.

Indications and Usage

FDG is a PET radiopharmaceutical that was first administered to human normal volunteers in 1976, and that has since been used in oncology imaging since the 1980s, in order to determine abnormal glucose metabolism and to assist in evaluating malignancy in patients with abnormalities found by other testing modalities or in patients with an existing diagnosis of cancer. FDG is indicated in PET for diagnostic use in patients for the evaluation of pulmonary nodules to distinguish benign from malignant and the evaluation of non-small cell and small cell lung cancers for staging and restaging and for the evaluation of colorectal cancer for recurrence, restaging, and distant metastases. For lung cancer evaluation, certain thoracic area non-cancerous lesions may show FDG uptake including acute and chronic infections (such as abscesses, tuberculosis and histoplasmosis), and inflammatory / granulomatous conditions (such as sarcoidosis, bronchiectasis, or post radiotherapy sites) that could mimic tumor accumulation. Absent or less intense relative uptake of FDG may be observed in specific lesions including bronchoalveolar, mucinous and lobular carcinoma as well as carcinoid and fibroadenoma sites. For colorectal cancer evaluation, certain abdominal / pelvic area non-cancerous lesions may show FDG uptake including sites of post radiation or post-surgical inflammatory response, lesion site flare following chemotherapy, colonic adenomas and bladder diverticula that could mimic tumor accumulation. Absent or less intense relative uptake of FDG may be observed in specific lesions including mucinous carcinoma. Lesion size may also affect detectability

based on relative FDG accumulation and PET imaging system resolution, as it has been shown that FDG PET imaging may have a lower sensitivity in evaluating lesion sizes of less than 1 cm.

Mechanism of Action

Fluorodeoxyglucose F 18 is a glucose analog that concentrates in cells that rely upon glucose as an energy source, or in cells whose dependence on glucose increases under pathophysiological conditions. Fluorodeoxyglucose F 18 is transported through the cell membrane by facilitative glucose transporter proteins and is phosphorylated within the cell to [18F] FDG-6-phosphate by the enzyme hexokinase. Once phosphorylated it cannot exit until it is dephosphorylated by glucose-6-phosphatase. Therefore, within a given tissue or pathophysiological process, the retention and clearance of Fluorodeoxyglucose F 18 reflect a balance involving glucose transporter, hexokinase and glucose-6-phosphatase activities. When allowance is made for the kinetic differences between glucose and Fluorodeoxyglucose F 18 transport and phosphorylation (expressed as the "lumped constant" ratio), Fluorodeoxyglucose F 18 is used to assess glucose metabolism. In comparison to background activity of the specific organ or tissue type, regions of decreased or absent uptake of Fluorodeoxyglucose F 18 reflect the decrease or absence of glucose metabolism. Regions of increased uptake of Fluorodeoxyglucose F 18 reflect greater than normal rates of glucose metabolism.

Radiation Exposure

Any exposure to radiation carries a very small risk of causing damage to tissues and the possibility of triggering a new cancer. However, the amount of radiation that each participant will be exposed to per (Fluorodeoxyglucose F18) PET scan is similar to the amount received from natural sources, such as the sun (background radiation) over the course of living in Denver for approximately 1.5 years. The FDG PET imaging will be performed at the Baseline visit and at EOT Visit. The administered dose of (Fluorodeoxyglucose F18) will be 5-10 mCi. For a (Fluorodeoxyglucose F18) dose of 10-15 mCi (185-370 MBq), the expected whole body effective dose is 6.3 mSv. In addition, the effective dose for a low dose head CT performed for localization and attenuation correction as part of the standard brain PET/CT protocol is 0.6 mSv. Thus, it is expected the trial participants will be exposed to about 7 mSv per fluorodeoxyglucose F18 scan, and when added to expected radiation exposure from flutemetamol F¹⁸ (Vizamyl, Optional), will remain well below the 50 mSv maximum annual dose of radiation exposure. On the pre-screening medical history form, participants and/or the study partner/caregiver will be asked to provide information whether the participant has been exposed to radiation during the past year (e.g. prior X-ray, CT, PET scans, etc.), so that the Study Physician and/or the Nuclear Medicine Imaging Professional can determine whether there will be a risk of the participant exceeding maximum allowed levels of radiation exposure.

Amyloid PET

The amyloid PET scan, for either entry criteria or as an optional sub-study, will use a common radiotracer (such as flutemetamol F¹⁸ (Vizamyl) which is a commonly used radiotracer that binds to β-amyloid plaques in the brain, as a biological marker of Alzheimer's disease. For evidence of β-amyloid neuritic plaques, if a participant opts to take part in the sub-study, they will receive a screening PET scan before the baseline visit, and a follow-up scan at the post-treatment follow-up visit, that will be assessed by a Nuclear Medicine Radiologist within the University of Colorado School of Medicine. The Nuclear Medicine Radiologist will remain blinded to participant identity and randomized test article group, and qualitative results, including any incidental findings, will reported to the Study Coordinator and Study Physician or qualified designee. If the PET scan is performed on the same day as the MRI scan, the PET scan will be performed after the MRI scan. The PET scans will be performed at an outpatient visit at the CU-RIC at CU-AMC. For quantification of the brain amyloid load, assessments will evaluate the screening PET scan before the baseline visit and another PET scan within +/- 7 days of the Follow-Up Visit approximately 45-days after the end of treatment with sargramostim or placebo. The change from the screening PET scan's SUVR to follow-up SUVR will be analyzed by a qualified nuclear medicine radiologist within the University of Colorado Hospital - Department of Radiology or by a contracted central reading facility (i.e., BioClinica, a

specialty clinical trial services provider) using the participant's MRI to reduce white matter contamination, thereby increasing the SUVR signal change by eliminating counts in the region that do not change (white matter). The amyloid PET scans and accompanying MRI scans will be stripped of any personal identifying information, containing only the trial's randomized ID number and date. The results of the PET quantitative analyses will not be used to make any treatment decisions.

Amyloid PET Imaging

The amyloid PET procedure will utilize the CU-RIC research PET scanner for human imaging studies. The Philips Gemini 64TF imaging system is located in Biosciences 3 building on the Anschutz Medical Campus at the University of Colorado.

Each study amyloid PET will take approximately 2 hours. A preliminary, 3-5 minute head CT scan will precede the administration of the radiotracer to aid in alignment and calibration, and adjust for attenuation effects. Immediately following, the participant will be comfortably positioned in a chair. An intravenous catheter will be inserted using standard aseptic technique. A 5 mCi (Vizamyl) intravenous injection will be administered. The participant will be placed on the scanning table and moved into the scanner. Dynamic images will be acquired for approximately 70 minutes. The IV catheter will be removed at the conclusion of the study and materials will be disposed of in biohazard containers or decay chambers until they can be safely disposed.

Indications and Usage

Vizamyl (flutemetamol F^{18}) is a radioactive imaging agent for Positron Emission Tomography (PET) imaging of the brain to estimate β -amyloid neuritic plaque density in adult patients with cognitive impairment who are being evaluated for Alzheimer's Disease (AD) and other causes of cognitive decline. A negative amyloid scan indicates sparse to no neuritic plaques, and is inconsistent with a neuropathological diagnosis of AD at the time of image acquisition; a negative scan result reduces the likelihood that a patient's cognitive impairment is due to AD. A positive amyloid scan indicates moderate to frequent amyloid neuritic plaques; neuropathological examination has shown this amount of amyloid neuritic plaque is present in patients with AD, but may also be present in patients with other types of neurologic conditions as well as older people with normal cognition. The use radiotracers such as Vizamyl has become a widely accepted amyloid imaging method in human subject research. Vizamyl received initial U.S. approval for use in research in 2013 and is in wide using in clinical trials and clinical practice.

Mechanism of Action

The radiotracer Vizamyl (flutemetamol F^{18}) is a F^{18} -labeled positron emission tomography (PET) imaging agent that binds with high affinity to the amyloid- β (A β) peptide fibrils that constitute amyloid plaques, and maps on to amyloid deposition in post-mortem studies ¹¹⁹. Vizamyl contains flutemetamol F 18, a molecular imaging agent that binds to β -amyloid aggregates and is intended for use with PET imaging of the brain. Chemically, flutemetamol F 18, is described as 2-[3-[18F]fluoro-4-(methylamino) phenyl]-6-benzothiazolol. It has the molecular formula C H 18FN OS.

Radiation Exposure

Any exposure to radiation carries a very small risk of causing damage to tissues and the possibility of triggering a new cancer. However, the amount of radiation that each participant will be exposed to per PET scan is similar to the amount received from natural sources, such as the sun (background radiation) over the course of living in Denver for approximately 1-2 years for Vizamyl. The optional amyloid PET imaging will occur at the Screening Visit and at the Follow-Up visit, or within a week thereof, depending upon scheduling availability. Administered dose of Vizamyl will be 5 mCi. For a Vizamyl dose of 5 mCi (185 MBq), the expected whole body effective dose is 5.92 mSv. In addition, the effective dose for a low dose head CT performed for localization and attenuation correction as part of the standard brain PET/CT protocol is 0.6 mSv. Thus, with two scans, it is expected the trial participants to be exposed to about 13 mSv

(Vizamyl) and when added to expected radiation exposure from FDG-PET, will remain well below the 50 mSv maximum annual dose of radiation exposure. On the pre-screening medical history form, participants and/or the participant's study partner/caregiver will be asked to provide information whether the participant has been exposed to radiation during the past year (e.g. prior X-ray, CT, PET scans, etc.), so that the Study Physician and/or the Nuclear Medicine Imaging Professional can determine whether there will be a risk of the participant exceeding maximum allowed levels of radiation exposure.

PET Safety Monitoring

All participants will be monitored carefully from injection until the conclusion of the imaging study. The PI and/or qualified designee will be available to consult if any questions arise during the PET scan. The research coordinator and Nuclear Medicine Technologist will be present through the entire duration of the PET scan, consistent with CU-RIC PET center guidelines. Each study participant will be contacted by phone approximately 2 (+/-1) business days after they were injected with the specific PET ligand to confirm their well-being and query them about any new adverse events. If any AE's are present they will be reviewed by the PI.

Sharing of optional Amyloid PET Information with Participant and/or Providers:

The study team does not plan to release (optional) amyloid scan results to study participants, as they are used for study analysis, not diagnostic or entry criteria.

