CSF assay may be performed examining $A\beta(1-42)$ and t-tau: $A\beta$ (1-42) ratio. The assay will be conducted during of screening and at the End of Treatment). Additionally, there will be an option utilizing Amyloid PET scans, performed using Vizamyl, produced at the CU-AMC / Pharmalogic cyclotron laboratory, which allows for amyloid-beta neuritic plaque density imaging. The Amyloid PET scans may be performed at Screening Visit and at the Follow-up Visit. Vizamyl is approved by the FDA for use in research and clinical application. For this protocol, the change from the screening scan's standardized uptake value ratio (SUVR) to follow-up SUVR will be similarly analyzed by a contracted central reading facility, using the participant's MRI to reduce white matter contamination, thereby increasing the SUVR signal change by eliminating counts in the region that do not change (i.e. white matter). The PET scans and accompanying MRI scans will be stripped of any personal identifying information, containing only the trial's randomized subject ID number and date. The results of the PET quantitative analyses will not be used to make any treatment decisions.

To assess the effect of sargramostim treatment, as compared to placebo, on AD related changes in peripheral blood and CSF biomarkers in individuals with mild-to-moderate AD.

Levels of AD-associated biomarkers in peripheral blood samples (collected at Baseline, 12, EOT and follow-up) and CSF samples (collected at Screening Visit and EOT) will be compared between placebo

controls and sargramostim treatment groups. The identification of circulating biomarkers in AD is a relatively new field, with inconsistent biomarker level results reported as increased, decreased, or unchanged between studies ¹²⁷. These mixed results mean that standardized levels for AD-associated circulating biomarkers have yet to be established. Therefore, we will compare observed biomarker levels from our project to other published levels to explore whether any similarities are observed. This comparison, as well as our own results, will add to the AD-associated blood and CSF biomarker fields of literature.

To assess the effect that ApoE genotype may have upon predicting sargramostim treatment outcomes in individuals with mild-to-moderate AD.

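### Section 8.3.3 takes the only planned amyloid PET head CT before the participant is moved to a chair, injected and placed on the scanning table, so the attenuation map may not match the head position in the PET images

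*Protocol*

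**What the plan says.** Protocol section 8.3.3, under Amyloid PET Imaging, lists the steps in this order:

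1. A 3-5 minute "head CT scan will precede the administration of the radiotracer to aid in alignment and calibration, and adjust for attenuation effects".
2. "Immediately following, the participant will be comfortably positioned in a chair".
3. A catheter is inserted, and "A 5 mCi (Vizamyl) intravenous injection will be administered".
4. "The participant will be placed on the scanning table and moved into the scanner".
5. "Dynamic images will be acquired for approximately 70 minutes".

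No further CT, head fixation or CT-to-PET registration is described. The amyloid Radiation Exposure text in the same section gives the tracer dose ("the expected whole body effective dose is 5.92 mSv"), adds 0.6 mSv for a head CT used for localization and attenuation correction, and puts the total for two scans at about 13 mSv.

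For the other tracer, the FDG PET Imaging Procedure in section 8.3.3 states: "After the fluorodeoxyglucose F18 dose is injected, a 3-5 minute head CT scan will be performed to aid in alignment and calibration". Image acquisition is the next step listed.

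The amyloid images feed an exploratory analysis in section 9.2.3, "the change from the screening scan's standardized uptake value ratio (SUVR) to follow-up SUVR". Sections 8.3.3 and 9.2.3 give MRI one role in that analysis, which is to limit the contribution of white matter.

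**The concern.** An attenuation CT is useful for the PET data to the extent that the head lies in the same place in both. In the written order the participant leaves the scanner for a chair after the CT and is positioned on the table after the injection. Nothing in the text restores or checks the head position recorded on the CT.

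If the map is displaced relative to the emission data, tissue and bone are assigned to the wrong lines of response and regional uptake is corrected by the wrong amount. The head is placed afresh at each visit, so this can happen at both screening and follow-up, and both scans enter the SUVR change. At stake is the precision of one exploratory amyloid measure. It is available only in participants who have amyloid PET, within a trial that expects about 42 completers.

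**Working it through.** **Step 1. Is another CT planned that would rescue the sequence?** The dose figures answer this. Inputs, all from section 8.3.3 (amyloid Radiation Exposure): tracer 5.92 mSv per scan, head CT 0.6 mSv, two scans, stated total about 13 mSv.

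Formula: total = scans x (tracer dose + number of CTs per scan x CT dose).

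| CTs per scan | Calculation | Total |
|---|---|---|
| 1 | 2 x (5.92 + 0.6) | 13.04 mSv |
| 2 | 2 x (5.92 + 1.2) | 14.24 mSv |

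One CT per scan reproduces the stated figure and two do not. The CT taken before injection is therefore the only one budgeted.

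**Step 2. Compare the two PET procedures.**

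| | Amyloid PET | FDG PET |
|---|---|---|
| CT relative to injection | before | after |
| Steps listed between CT and images | chair, catheter, injection, placement on table | none |
| Stated purpose of CT | alignment, calibration, attenuation | alignment, calibration, attenuation |

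The purpose is the same, but only the amyloid order puts a change of position between the CT and the images. No reason is given for the difference.

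**Step 3. Can the added error be sized?** No. The documents give neither an SD for SUVR change nor a size for the misalignment. Suppose, purely as an illustration, that misalignment adds independent error to the change with an SD equal to a fraction r of the SD of SUVR change. The variance is then multiplied by 1 + r^2:

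- r = 0.10: 1 + 0.01 = 1.01, a rise of 1%
- r = 0.25: 1 + 0.0625 = 1.0625, a rise of about 6%
- r = 0.50: 1 + 0.25 = 1.25, a rise of 25%

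The result depends entirely on r, which is assumed. These values show the form of the effect and do not estimate it.

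**Step 4. Does the reorder change the dose?** With one CT per scan taken after positioning, the total is still 2 x (5.92 + 0.6) = 13.04 mSv.

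**The case against.** The strongest reply is that a CT taken before repositioning is not useless. Software can register it to the PET data before attenuation correction. The protocol does not exclude this, and an imaging manual might specify it. This stands in part: mismatch is a possibility that the written order leaves open, not an established fact. A reader might infer that the CT cannot serve its purpose at all, and the documents do not support that.

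Four other stronger readings are tempting:

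- **That the FDG and amyloid procedures contradict each other.** They are separate procedures for separate tracers and may differ. The FDG text places the CT after injection and before the images, but it says nothing about table position or about the interval between CT and images. It shows that another order is in use, not that the amyloid text is inconsistent with it.
- **That the loss of precision is large.** Assuming an SD of SUVR change of 4% and an added 2-4% per scan gives variance factors from (16 + 2 x 4)/16 = 1.5 to (16 + 2 x 16)/16 = 3.0. None of these inputs is in the documents, so the factor, and any loss of effective sample size drawn from it, follows from the assumptions alone.
- **That entry decisions are compromised.** Section 6.1.1 bases PET entry on the investigator's read of the scan as positive, and section 8.3.3 has the radiologist report qualitative results. No SUVR threshold governs entry, and nothing shows that a small quantitative error would change a read.
- **That the treatment comparison is biased.** The same order applies in both arms and the readers are blinded, so the expected effect is noise.

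The endpoint is also only exploratory. Neither the safety primary nor the MMSE secondary endpoint uses these images, and the quantitative PET results do not guide treatment.

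**Conclusion.** The point holds, at low severity. Followed literally, section 8.3.3 acquires the only planned attenuation and alignment CT before the head is repositioned for PET, and it provides no registration step. This works against the purpose the protocol itself gives for the CT. It exposes the exploratory SUVR change to avoidable measurement error in participants who have amyloid PET. The one-CT conclusion rests on the protocol's own dose arithmetic (13.04 mSv against about 13 stated). That a mismatch may follow is an inference from the chair and table steps, and its size cannot be derived from the documents. No bias between arms is expected.

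**What to change.** Reword the amyloid PET steps in section 8.3.3 so that the single head CT is acquired after the participant is in final position on the scanning table, adjacent to the emission scan and without leaving the table. Require the same order at screening and follow-up. The FDG text, which already lists the CT after injection and before the images, can serve as a model for the order; the condition about staying on the table has to be added. If the imaging site already works this way, the same edit brings the text into line with practice.

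The cost is a wording change. There is still one CT per scan, the two-scan dose stays at about 13 mSv, and no staff or visit time is added.
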